## PASS Information

Title	A Prospective, Registry-based, Observational Study to Assess Maternal and Fetal Outcomes Following Exposure to Galcanezumab
Version identifier	1.0
Date of last version	N/A
EU PAS Register No:	EUPAS28151
Active substance	Galcanezumab; ATC code: N02CX08
Medicinal product(s):	Galcanezumab-gnlm 120-mg solution
Product reference:	EU/1/18/1330
Procedure number:	EMA/H/C/004648
Marketing authorisation holder(s)	Eli Lilly and Company
Joint PASS	No
Research question and objectives	
The purpose of the study is to prospectively evaluate pregnancy, maternal and infant outcomes through 12 months of age among women exposed to galcanezumab during pregnancy, as well as in two galcanezumab-unexposed comparison groups.
 
The primary objective is to describe the occurrence of congenital malformations (main outcome), pregnancy outcomes, maternal pregnancy complications, infant outcomes at birth and infant events of interest up to 1 year post-delivery among women exposed to galcanezumab, as well as in 1) women with migraine not exposed to CGRP antagonists and 2) women without migraine:
 
 
• Congenital malformations (major and minor)
 
• Pregnancy outcomes (recognized spontaneous abortions, molar pregnancy, ectopic pregnancy, elective terminations, stillbirths)
 
• Maternal pregnancy complications (pre-eclampsia, hypertension)
 

Approval Date: 22-Nov-2019 GMT

	
 
• Infant outcomes (preterm birth and small-for-gestational-age births)
 
• Infant events of interest (postnatal growth and development up to one year of age)
 
 
The secondary objective is to estimate, where statistically feasible, the relative occurrence of congenital malformations, pregnancy, maternal, and infant outcomes among women exposed to galcanezumab as compared to 1) women with migraine not exposed to CGRP antagonists and 2) women without migraine.
 
Exploratory objective: Additional available published external comparator data sources in patients/women with migraine and the general population for estimates of selected outcomes will be evaluated to contextualize observed outcome occurrences in the registry.

Country(-ies) of study	USA
Author	
PPD
 

## 2. List of Abbreviations

Term	Definition
AEs	Adverse events
AR	Adverse reaction
CDER	Center for Drug Evaluation and Research
CDC	Centers for Disease Control and Prevention
CEDD	Corrected estimated date of delivery
CFR	Code of Federal Regulations
CGRP	Calcitonin gene-related peptide
CMA	Central monitoring associate
CRF	Case report form
EDC	Electronic data capture
FDA	Food and Drug Administration
GPP	Good Pharmacoepidemiology Practice
HCP	Healthcare provider
HIPAA	Health Insurance Portability and Accountability Act
ICSR	Individual Case Safety Reports
IHS	International Headache Society
IRB	Institutional Review Board
LMP	Last menstrual period
MACDP	Metropolitan Atlanta Congenital Defects Program
MCM	Major congenital malformation
NVSS	National Vital Statistics System
PLLR	Pregnancy and Lactation Labeling Rule
PMC	Post marketing commitment
RCC	Registry Coordinating Center
SAB	Spontaneous abortion

SAC	Scientific Advisory Committee
SAE	Serious adverse event
SAP	Statistical analysis plan
SGA	Small-for- gestational- age
SOP	Standard Operating Procedure

---

### 3. Responsible Parties

Not applicable.

## 4. Abstract

- Title: A Prospective, Registry-based, Observational Study to Assess Maternal and Fetal Outcomes Following Exposure to Galcanezumab

Version: 1.0

Main author: PPD

- Rationale and background: Migraine prevalence is highest in women during childbearing years (Buse et al. 2012). There is often a medical need for preventive treatment of migraine during pregnancy, with treatment decisions based on clinical judgement of the benefits and the potential harms (Cassina et al. 2010). Pregnant women were not included in the galcanezumab clinical development program. The population of pregnant women treated with galcanezumab is therefore one which warrants further characterization, as effects on the fetus after exposure in utero are unknown. Accordingly, this study has been mandated by the FDA to monitor pregnancy and infant outcomes.
- Research question and objectives: The purpose of the study is to prospectively evaluate pregnancy, maternal, and infant outcomes through 12 months of age among women exposed to galcanezumab during pregnancy, as well as in two galcanezumab-unexposed comparison groups.

The primary objective is to describe the occurrence of congenital malformations (main outcome), pregnancy outcomes, maternal pregnancy complications, infant outcomes at birth and infant events of interest up to 1 year post-delivery among women exposed to galcanezumab, as well as in 1) women with migraine not exposed to CGRP antagonists and 2) women without migraine:

- Congenital malformations up to one year of age (major and minor malformations)
- Pregnancy outcomes (recognized spontaneous abortions, molar pregnancy, ectopic pregnancy, elective terminations, stillbirths)
- Maternal pregnancy complications (pre-eclampsia, hypertension)
- Infant outcomes at birth (preterm birth and small-for-gestational-age births)
- Infant events of interest up to one year of age (postnatal growth and development)

The secondary objective is to estimate, where statistically feasible, the relative occurrence of congenital malformations, pregnancy, maternal, and infant outcomes among women exposed to galcanezumab as compared to 1) women with migraine not exposed to CGRP antagonists and 2) women without migraine.

Exploratory objective: Additional available published external comparator data sources in women with migraine and the general population for estimates of selected outcomes will be evaluated to contextualize observed outcome occurrences in the registry.

- Study design: This study is a prospective, observational, exposure-registration study in line with the current FDA guidance for designing and implementing pregnancy exposure registries (FDA 2002).
- Population: The study population will include pregnant women within the US who were treated with galcanezumab as part of routine care at any time during pregnancy or up to 4 months prior to conception, as well as pregnant women with migraine not exposed to CGRP antagonists and pregnant women without migraine.

The minimum eligibility criteria required for enrollment are as follows:

**Inclusion:**

- Pregnant at the time of enrollment
- Sufficient information to confirm eligibility for either the galcanezumab, unexposed to CGRP antagonist, or general population cohort
  - Galcanezumab cohort: at least one injection of galcanezumab during the pre-pregnancy or pregnancy period (as defined in Section 9.3.1) without any other CGRP antagonist exposure during this time, and at which date
  - Unexposed to CGRP antagonist cohort: no exposure to a CGRP antagonist during the pre-pregnancy period (as defined in Section 9.3.1)
  - General population (without migraine) cohort: no diagnosis of migraine
- Sufficient information to determine whether the outcome of pregnancy is known at the time of registry reporting (e.g., results of genetic testing and/or ultrasound)
- Reporter (e.g., participant, maternal healthcare reporter (HCP)) contact information to allow for follow-up
- Permission to contact the patient's and her infant's HCPs
- Patient informed consent to participate

**Exclusion:**

- Patients with known pregnancy outcomes at the time of enrollment
- Variables:

*Exposure:* treatment with galcanezumab at any time during pregnancy or up to 4 months prior to conception.

*Outcomes:*

- Congenital malformations: major and minor malformations
- Pregnancy outcomes: recognized spontaneous abortions, ectopic pregnancy, molar pregnancy, stillbirths, elective terminations

- Maternal pregnancy complications: preeclampsia and hypertension in pregnancy
- Infant outcomes at birth: preterm birth, small for gestational age infants
- Infant events of interest (up to one year of age): postnatal growth and development
- Data sources: The pregnant woman and appropriate members of her and her infant's health care team will serve as data reporters to the study. The study is strictly observational; patient care and treatment regimens will be determined by the treating HCP.
- Study size: The study aims to enroll a minimum of 420 prospectively enrolled evaluable (i.e., those for whom outcome of pregnancy including presence/absence of any congenital malformations was obtained) pregnant women with galcanezumab exposure, as well as 420 untreated migraine controls (i.e., not treated with galcanezumab or other CGRP antagonists but *may* have been treated with other prescribed or over-the-counter migraine therapies) and 420 non-migraine, general population controls (i.e., do not suffer from migraines).

Data analysis: Demographic and baseline characteristics will be summarized with descriptive statistics for the galcanezumab exposed group as well as for the two comparison groups.

Proportions and 2-sided, 95% confidence intervals will be calculated using the exact binomial distribution for prevalence of congenital malformations among evaluable patients, preterm birth and SGA among patients with live births, preeclampsia and hypertension in pregnancy and infant growth and development through one year. Rates will be presented overall and stratified by timing of exposure.

- Where statistically feasible, the relative occurrence of maternal, pregnancy and infant outcomes among women exposed to galcanezumab as compared to 1) women with migraine not exposed to CGRP antagonists and 2) women without migraine will be estimated.
- Milestones: The study will be open for enrollment beginning 01 March 2020. The estimated end of data collection is 30 November 2032, and the Final Study Report will be submitted 30 November 2033.

## 5. Amendments and Updates

Not applicable.

## 6. Milestones

Milestone	Planned date
Start of data collection	01 March 2020
End of data collection	30 November 2032
Interim reports	Annually beginning 30 November 2020, ending 30 November 2031
Final report of study results	30 November 2033

## 7. Rationale and Background

Migraine is a recurrent headache disorder characterized by painful attacks lasting 4 to 72 hours usually accompanied by other symptoms including nausea, vomiting, sensitivity to light and sound, and changes in vision (Katsarava et al. 2012). It is a spectrum of illness, with clinical symptoms that vary along a continuum from episodic migraine to chronic migraine. Chronic migraine and episodic migraine are part of the spectrum of migraine disorders, but they are distinct clinical entities as classified by International Classification of Headache Disorders–3rd edition, (ICHD 2018). In the United States (US) the prevalence of self-reported migraine and severe headache was 15.3% over a 3-month period. Migraine disproportionately affects women of child-bearing age and is among the top 5 reasons for emergency department visits. Globally, migraine is ranked second as a cause of disability expressed as years lived with disability (GBD 2016 Disease and Injury Incidence and Prevalence Collaborators 2017). Cluster headache is one of the most severe primary headache syndromes and is characterized by recurrent attacks of intense headaches on one side of the head, frequently associated with pain behind or around one eye, restlessness and agitation (Ashkenazi et al. 2011). A cluster period generally lasts from 6 to 12 weeks and a single attack typically lasts between 15 minutes and three hours (Headache Classification Committee of the International Headache Society 2018). Cluster headache has been associated with seasonal changes with higher incidence of attacks reported in the fall and spring (citation). The International Headache Society (IHS) classified cluster headache into two major temporal types: episodic (85–90%) and chronic (10–15%). The prevalence of overall cluster headache is approximately 1% and it mostly affects men with overall male-to-female ratio of 4 (Fischera et al. 2008). Age of onset is  $30.2 \pm 13.8$  years (Manzoni et al. 2016) with the highest prevalence in the 35 to 45 age group (53.3%) (Jurno et al. 2018).

Galcanezumab is a humanized IgG4 monoclonal antibody that binds calcitonin gene-related peptide (CGRP) and prevents its biological activity without blocking the CGRP receptor. Elevated blood concentrations of CGRP have been associated with migraine or cluster headache attacks (Durham et al. 2008). Three placebo-controlled phase-III clinical trials demonstrated a reduction in the number of monthly migraine headache days for galcanezumab in patients with episodic migraine (EVOLVE-1 and EVOLVE-2) and patients with chronic migraine (REGAIN) (Skljarevski et al. 2018, Stauffer et al. 2018, Detke et al. 2018). Another placebo-controlled phase-III study of patients with episodic cluster headache also demonstrated a significant reduction of weekly cluster headache attacks from baseline across weeks 1-3 comparing galcanezumab with placebo; results were presented at the 2018 American Headache Society annual meeting. Emgality™ (galcanezumab), a once-monthly, subcutaneous 120 mg injection, with a 240 mg loading dose, which has a half-life of 27 days, has received approval from the FDA for the preventive treatment of migraine in adults and marketing authorization from European Commission for the prophylaxis of migraine in adults who have at least 4 migraine days per month.

As is standard, pregnant women were not included in the clinical development program; however, a number of pregnancies occurred in women treated with galcanezumab in the clinical trials: **PPD**

## PPD

Embryo-fetal development studies conducted in rats and rabbits at exposures up to 29 times the highest proposed clinical dose of 300 mg revealed no evidence of harm to the developing fetus and there were no effects on survival, growth, sexual maturation, behavior, or reproduction in offspring exposed to galcanezumab in utero and through lactation at exposures up to 16 times the highest proposed clinical dose of 300 mg in the prenatal and postnatal development study in rats.

The current nonclinical data and the low number of pregnancy outcomes in humans are insufficient to draw conclusions about the effect or safety of galcanezumab exposure during human pregnancy. However, migraine prevalence is highest in women aged 18 to 49 years (Buse et al. 2012) during typical childbearing years. There is often a medical need for preventive treatment of migraine during pregnancy, with treatment decisions based on clinical judgement of the benefits and the potential harms (Cassina et al. 2010). It is anticipated that given the treated patient population and the long half-life of galcanezumab, exposure during pregnancy will occur in the post-authorization setting and thus, further study is warranted.

Reviews of studies evaluating pregnancy outcome in women with migraine generally conclude that migraine, treated or untreated, probably has no effect on most pregnancy outcomes, including risk of congenital anomalies (MacGregor 2012; Menon and Bushnell 2008). Women with migraine have been reported to be at increased risk of developing hypertensive disorders such as pre-eclampsia in pregnancy compared to women without migraine (Banhidly et al. 2007; Facchinetti et al. 2009) which is associated with an increased risk of low birth weight (preterm birth, small for gestational age infant) (Adeney et al. 2005, Simbar et al. 2010, Facchinetti et al. 2009). In the migraine population, more severe migraine, defined by greater frequency and intensity, is associated with increased prevalence of cardiovascular comorbidity and comorbid affective disorders such as anxiety and depression (Chen et al. 2012; Goulart et al. 2014).

Another challenge for evaluation of pregnancy, maternal, and fetal/infant outcomes is the known association of some prophylactic migraine medications with congenital malformations and other study outcomes. Therefore, careful selection of comparison populations of women with migraine treated with preventive migraine medication is needed to accurately contextualize event rate .

This prospective, registry-based, observational study to assess maternal and fetal outcomes following exposure to galcanezumab will fulfill a post marketing commitment (PMC) requested by the Food and Drug Administration's (FDA) Center for Drug Evaluation and Research (CDER) and is designed to evaluate pregnancy outcomes as well as maternal and infant events of interest among women exposed to galcanezumab during pregnancy. The design and outcomes are chosen following the FDA request, FDA guidance on pregnancy exposure registries (FDA, 2002), and experience from other pregnancy studies.

## 8. Research Question and Objectives

The purpose of the study is to prospectively evaluate pregnancy, maternal and infant outcomes through 12 months of age among women exposed to galcanezumab during pregnancy, as well as in two galcanezumab-unexposed comparison groups.

The primary objective is to describe the occurrence of congenital malformations (main outcome), pregnancy outcomes, maternal pregnancy complications, infant outcomes at birth and infant events of interest up to 1 year post-delivery among women exposed to galcanezumab, as well as in 1) women with migraine not exposed to CGRP antagonists and 2) women without migraine:

- Congenital malformations (major and minor)
- Pregnancy outcomes (recognized spontaneous abortions, molar pregnancy, ectopic pregnancy, elective terminations, stillbirths)
- Maternal pregnancy complications (pre-eclampsia, hypertension)
- Infant outcomes (preterm birth and small-for-gestational-age births)
- Infant events of interest (postnatal growth and development up to one year of age)

The secondary objective is to estimate, where statistically feasible, the relative occurrence of congenital malformations, pregnancy, maternal, and infant outcomes among women exposed to galcanezumab as compared to 1) women with migraine not exposed to CGRP antagonists and 2) women without migraine.

Exploratory objective: Additional available published external comparator data sources in women with migraine and the general population for estimates of selected outcomes will be evaluated to contextualize observed outcome occurrences in the registry.

## 9. Research Methods

### 9.1. Study Design

This study is a prospective, observational, exposure registry of US women exposed to galcanezumab during pregnancy. Two comparison groups will also be enrolled: 1) migraine controls not treated with CGRP antagonists (but who may have been treated with other prescribed or over-the-counter migraine therapies) and 2) general population controls (without migraine). Additional available published external comparator data in women with migraine and other population-based surveillance data will be evaluated to contextualize the registry findings.

The study is designed according to the current FDA guidance for designing and implementing pregnancy exposure registries (FDA 2002), and is strictly observational.

### 9.2. Setting

This study is US based.

#### 9.2.1. Study Period

The study will be open for enrollment beginning March 2020. The data collection process for each participant will begin at enrollment (during pregnancy), and follow-up will occur at the end of the second trimester (approximately 24 weeks' gestation) and/or at pregnancy outcome (delivery or early termination). The second trimester pregnancy follow-up may not be applicable for women who enroll late in pregnancy. If a live birth is reported, the Registry conducts follow-up at 4 and 12 months of age.

An annual interim study report, reviewed by the SAC, will be submitted to the Center for Drug Evaluation and Research (CDER) beginning November 2020. The Interim Report summarizes the status and the cumulative data, current to the most recent annual data cutoff period. The estimated end of data collection is 30 November 2032. The last annual report will be submitted November 2031 and the final report will be submitted November 2033.

#### 9.2.2. Study Participants

The study population will include pregnant women within the US who were treated with galcanezumab as part of routine care at any time during pregnancy or up to 4 months prior to conception, as well as pregnant women with migraine not exposed to CGRP antagonists and pregnant women without migraine. Eligible pregnant women may self-enroll or voluntarily be enrolled by their HCP. Enrollment should occur as early in pregnancy as possible, preferably before any prenatal testing has occurred.

Enrollment and data collection will be coordinated through the Registry Coordination Center (RCC). The minimum eligibility criteria required for enrollment are as follows:

Inclusion:

- Pregnant at the time of enrollment

- Sufficient information to confirm eligibility for either the galcanezumab, unexposed to CGRP antagonist, or general population cohort
  - Galcanezumab cohort: at least one injection of galcanezumab occurred during the pre-pregnancy or pregnancy period (as defined in Section 9.3.1) without any other CGRP antagonist exposure during this time and at which date
  - Unexposed to CGRP antagonist cohort: no exposure to a CGRP antagonist during the pre-pregnancy period (as defined in Section 9.3.1)
  - General population (without migraine) cohort: no diagnosis of migraine
- Sufficient information to determine whether the outcome of pregnancy is known at the time of registry reporting to determine whether the pregnancy exposure reported to the registry is prospective (i.e., before the outcome or perceived outcome of pregnancy is known) and eligible for enrollment
- Reporter (e.g., participant, maternal HCP) contact information to allow for follow-up
- Permission to contact the patient's and her infant's HCPs
- Patient informed consent to participate

Exclusion:

- Retrospective (i.e., a pregnancy exposure to the Registry drug reported after the pregnancy has ended or for an ongoing pregnancy in which an abnormal condition was identified on a prenatal test) cases are ineligible for enrollment
- Women under 18 years of age

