### **9.3. Variables**

#### **9.3.1. Exposure of Interest**

The exposure of interest is treatment with galcanezumab at any time during pregnancy or up to 4 months prior to conception. Any injection of galcanezumab within 4 months prior to the LMP is considered exposed due to its long half-life. Data will be collected regarding dates of treatment and number of doses. The trimester of exposure will also be captured.

CGRP antagonist-unexposed women with migraine will not have been treated with CGRP antagonists at any time during pregnancy or up to 4 months prior to conception, but may have been treated with other prescribed or over-the-counter migraine therapies.

Treatment is not under control of the study but administered solely at the discretion of the pregnant woman's treating HCP and as part of routine clinical care. Only data that are routinely recorded in the course of usual care among women treated with galcanezumab during pregnancy will be collected.

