e Contact to obtain Medical Information Release Form for Pediatrician if not previously obtained.

f Collect only if unable to collect at birth from Maternal HCP contact.

g Applicable for galcanezumab exposed group only.

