### **9.4.3. Operational Exposure Definition**

When a pregnant woman enrolls in the study, she will be asked when she was last treated with galcanezumab. When a pregnant woman is enrolled by her HCP, the HCP will provide this information. The pregnant woman will then be asked to provide a medical release that allows the RCC to confirm galcanezumab treatment with the appropriate source. Reported galcanezumab injection at any time during pregnancy (from four months prior to LMP until pregnancy outcome) will constitute a fetal exposure. Galcanezumab exposure will be further categorized by earliest trimester of exposure.

For this study, gestational weeks will be estimated from the most reliable EDD as reported by the HCP or the pregnant woman. If a CEDD is provided by the HCP, it will be used instead. The date of conception will be calculated as the most reliable EDD minus 38 weeks. If the EDD is not available or never estimated, the first day of the LMP may be used to estimate gestational age. The second trimester will be considered to begin at week 14 after LMP, and the third trimester at week 28. If there is a discrepancy between gestational age calculated from LMP and reported gestational age, the HCP will be asked to verify the data.

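### The enrolment criterion for the CGRP-unexposed cohort bars CGRP antagonists only before pregnancy, contradicting Section 9.3.1, which bars them during pregnancy as well

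*Protocol*

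**What the plan says.** Section 9.2.2 of the protocol sets one admission rule per cohort, as part of the minimum a woman must meet to enrol.

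- Galcanezumab cohort: "at least one injection of galcanezumab occurred during the pre-pregnancy or pregnancy period (as defined in Section 9.3.1", with no other CGRP antagonist in that time.
- Migraine comparator: "Unexposed to CGRP antagonist cohort: no exposure to a CGRP antagonist during the pre-pregnancy period (as defined in Section 9.3.1". The Abstract (Section 4, Inclusion) has the same limit: "no exposure to a CGRP antagonist during the pre-pregnancy period (as defined in Section 9.3.1".
- General-population comparator: "General population (without migraine) cohort: no diagnosis of migraine". It sets no condition on CGRP antagonists.

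Section 9.3.1, which the first two rules cite, defines exposure over both windows: "The exposure of interest is treatment with galcanezumab at any time during pregnancy or up to 4 months prior to conception". It then says that the CGRP-unexposed women with migraine "will not have been treated with CGRP antagonists at any time during pregnancy or up to 4 months prior to conception".

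Section 9.4.3 makes the same point for galcanezumab: "Reported galcanezumab injection at any time during pregnancy (from four months prior to LMP until pregnancy outcome) will constitute a fetal exposure".

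Section 8 describes both comparison groups as not exposed to galcanezumab.

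**The concern.** A comparator labelled unexposed should be free of the exposure over the whole period in which the protocol counts exposure. The rule that admits women to the migraine comparator covers only the first part of that period. It therefore conflicts with the section that it cites.

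The people applying the rule will often have only the criteria in front of them. Women may self-enrol, and Section 9.2.3.1 relies on dedicated reporters who are not site investigators and who commit to enrolling all eligible, consenting patients.

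The secondary objective, which compares galcanezumab with each internal comparator, is what is at stake. If the drug raises a risk, exposed women counted as unexposed raise the comparator's risk and shrink the ratio. For a safety registry that is the unsafe direction. The comparator proportions reported under the primary objective would also describe a mixed group.

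**Working it through.** The point is textual, and the plan has no figure to reproduce.

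**Step 1: are the two windows distinct?** The galcanezumab criterion joins pre-pregnancy and pregnancy with the word *or*. The next bullet keeps only pre-pregnancy. Within one list, then, pre-pregnancy cannot be read to include pregnancy.

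**Step 2: does the cross-reference repair it?** Grammatically, the reference to Section 9.3.1 qualifies only the term *pre-pregnancy period*. Section 9.3.1 does not define that term by name. A reader who follows the reference finds the full window there, but finds it contradicting the criterion.

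**Step 3: does an exclusion close the gap?** No. The Abstract excludes women whose pregnancy outcome is already known. Section 9.2.2 excludes retrospective cases and women under 18. Neither list mentions CGRP antagonists.

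**Step 4: what follows literally?**

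| First CGRP-antagonist use | Galcanezumab rule | Unexposed rule, Section 9.2.2 | Section 9.3.1 |
|---|---|---|---|
| Galcanezumab, pre-pregnancy window | met | not met | exposed |
| Galcanezumab, only after conception | met | **met** | exposed |
| Another CGRP antagonist, only after conception | not met | **met** | not CGRP-unexposed |

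In the second row one woman fits two cohorts. In the third, a woman who cannot be in the exposed cohort is admitted to the unexposed one, and Section 9.3.1 forbids that.

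**Step 5: the general-population rule.** It asks only for no migraine diagnosis. Section 9.2.3.1 also recruits through providers who treat cluster headache, so a woman without migraine but with CGRP-antagonist use is not barred by the criterion. Section 8 nevertheless calls this group galcanezumab-unexposed.

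**Step 6: direction, as an assumed illustration only.** Let p be the comparator risk, 2 the true ratio (the target in Section 9.5), c the share of comparator women who are in fact exposed, and f the fraction of those who carry the doubled risk. The comparator risk becomes p(1 − cf) + 2p·cf = p(1 + cf), so the observed ratio is 2/(1 + cf).

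- f = 1: c = 5%, 10% and 20% give 2/1.05 = 1.90, 2/1.10 = 1.82 and 2/1.20 = 1.67.
- f = 0.25, c = 5%: 2/1.0125 = 1.98.

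The documents give neither c nor f. Section 9.7.2 says that most structural defects arise in the first trimester, so f for malformations may be well below 1 when first use comes later in pregnancy. The sums show the direction and how strongly the size depends on the assumptions. They are not an estimate.

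**The case against.** The strongest reply is that nobody would be misled. The population sentence that opens Section 9.2.2, Section 9.2.4.1 and Section 9.3.1 all describe women with migraine who are not exposed to CGRP antagonists, and the criterion cites Section 9.3.1. This stands as evidence of intent and makes a drafting omission the likely explanation. It does not make the criterion correct: the criterion is the text applied at enrolment, it appears twice, and it conflicts with its own reference.

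Four stronger readings are tempting, and the documents do not support them.

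- *The comparator need not have migraine.* The bullet does not say so, but the population sentence in the same section and Sections 9.2.4.1 and 9.3.1 do. Naming migraine in the bullet is tidying.
- *Later exposure in comparator women would go unseen.* Table 1 does mark the galcanezumab row "Applicable for galcanezumab exposed group only". The concomitant-medication row has no such limit. It records start and stop dates at enrolment and registration and is updated at the interim and outcome contacts. Section 9.4.1.2 asks about migraine medications in particular.
- *Every relative estimate is biased.* Comparisons with the external MACDP and NVSS figures do not use the internal comparators and are unaffected.
- *Exposed women without migraine will enter the general-population group in numbers.* Section 9.4.3 already classes any galcanezumab injection in the window as a fetal exposure. Section 7 puts cluster headache at about 1% prevalence, with four men affected for each woman. The route is narrow. Section 9.4.3, however, speaks only of galcanezumab and does not cover other CGRP antagonists.

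How to handle a woman who starts treatment after enrolment may be set out in the SAP, which is not shown, so its absence from the protocol is not itself a fault. A SAP does not, however, correct the protocol's eligibility text.

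**Conclusion.** The contradiction holds. The unexposed criterion in Sections 4 and 9.2.2 covers one window where Section 9.3.1 requires two, and no other criterion closes the gap. Followed literally, it admits women first treated after conception.

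If treatment raises risk, the effect is to pull the internal relative estimates towards no effect. The size cannot be given, because the documents contain no rate of first CGRP-antagonist use during pregnancy and no basis for assigning a risk to other drugs in the class. Given the clear intent elsewhere and the dated medication records, it may be small.

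This is an error in an operative rule, most likely of drafting. It is not evidence that the design means to admit exposed women.

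**What to change.** 1. In Sections 4 and 9.2.2, reconcile the unexposed criterion with Section 9.3.1: migraine, and no CGRP antagonist in either the pre-pregnancy or the pregnancy window of that section.
2. In the same two places, add the no-CGRP-antagonist condition over those windows to the general-population criterion, since Section 8 calls both comparators galcanezumab-unexposed.
3. State, in the protocol or the SAP, that a comparator woman whose concomitant-medication record shows a CGRP antagonist in those windows is not counted as unexposed in the comparative analyses. This is needed because eligibility can be checked only up to the day of enrolment.

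No new form item is needed, since Table 1 already collects dated medication records in all cohorts. No person-time rule is needed either, because the planned estimates are binomial proportions. The cost is a few lines of text and the removal of a few comparator women.
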